9.7.3. Analysis of the outcome measures

9.7.3.1. Comparison with internal comparator cohorts

Formal quantitative comparisons of prevalence rates of the outcomes of interest will be conducted between the study cohorts. The prevalence rates of the outcomes of interest will be calculated as described in Section 9.7.3.3.

For each outcome, if the number of events permits, results will be presented for unadjusted and adjusted models. Summary statistics (relative risk) will be reported along with their 95% CIs and p-values. For the primary outcome, a p-value <0.05 will be considered statistically significant. Exact methods will be used to calculate crude (unadjusted) relative risks for binary outcomes, including MCM, minor congenital malformation, SAB, elective termination, TOPFA, stillbirth, pre-eclampsia, eclampsia, gestational hypertension, gestational diabetes, preterm birth, SGA, postnatal growth deficiency, and infant developmental delay.

Adjusted methods will incorporate weights estimated using the IPW method to balance the cohorts with regard to observable covariates (Section 9.7.3.4). For each binary outcome, a weighted generalized linear model using a binomial family and a log (relative risk) link will be employed to estimate an adjusted relative risk.

PFIZER CONFIDENTIAL

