9.7.3.3. Calculation of outcome prevalence

Prevalence rates of the outcomes of interest will be calculated according to the conventions described in Table 4. In general, the prevalence of each outcome will be calculated by dividing the number of cases of the outcome by the appropriate denominator for that particular outcome, based on clinical knowledge and/or the methodology used by the external comparator. Prevalence is preferred over incidence when examining pregnancy outcomes, such as congenital malformations, because incidence cannot be reliably estimated given the complexities in the reproductive process.⁶⁷

For most outcomes, the main analysis population (denominator) will be the number of pregnant women with pregnancy outcome data, the number of live births, or the number of infants with follow-up data at the timepoint of interest, as appropriate; however, for some outcomes, the main analysis population (denominator) will be restricted based on certain relevant factors:

- For MCM, prevalence in the rimegepant-exposed cohort will be calculated among the subset of women who are exposed during the first trimester.
- For MCM, prevalence will be calculated among live births for the primary analysis, and a secondary analysis will be conducted among live births and fetal losses.
- For preterm birth, SGA, and postnatal growth deficiency, prevalence will be calculated among singleton live births due to the higher risk of these outcomes in twins and higher-order multiples.
- For live birth and infant outcomes (ie, preterm birth, SGA, postnatal growth deficiency, and infant developmental delay), prevalence will be calculated among live births/infants without MCMs.
- For postnatal growth deficiency, infants born preterm or SGA will be excluded from the main analysis population (denominator).
- For infant developmental delay, infants born preterm will be excluded from the main analysis population (denominator).
- For SAB and preterm birth, prevalence will be calculated among the subset of women who are enrolled in the registry prior to 20 and 37 gestational weeks, respectively.
- For some outcomes, prevalence will be calculated at multiple timepoints. For example, postnatal growth deficiency and infant developmental delay will be assessed at 2, 4, 6, and 12 months of

PFIZER CONFIDENTIAL

infant age. At each timepoint, prevalence will be calculated among infants with data available for the particular outcome at that timepoint.

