Primary analysis between internal cohorts	Pre-eclampsia among women with pregnancy outcome data	Women with pregnancy outcome data
Eclampsia	·	
Primary analysis between internal cohorts	Eclampsia among women with pregnancy outcome data	Women with pregnancy outcome data
Comparison with external comparator ⁶¹	Eclampsia among live births	Live births among women with pregnancy outcome data
Pre-eclampsia/eclampsia	•	
Primary analysis between internal	Pre-eclampsia or eclampsia among	Women with pregnancy outcome

PFIZER CONFIDENTIAL

Outcome	Numerator	Denominator
cohorts	women with pregnancy outcome data	data
Comparison with external comparator (Pfizer Study C4951006)	Pre-eclampsia or eclampsia among women with pregnancy outcome data	Women with pregnancy outcome data
SAB		
Primary analysis between internal cohorts	SABs among women with pregnancy outcome data who are enrolled (and exposed, if applicable) prior to 20 gestational weeks	Women with pregnancy outcome data who are enrolled (and exposed, if applicable) prior to 20 gestational weeks
Comparison with external comparator (Pfizer Study C4951006)	SABs among women with pregnancy outcome data who are enrolled (and exposed, if applicable) prior to 20 gestational weeks	Women with pregnancy outcome data who are enrolled (and exposed, if applicable) prior to 20 gestational weeks
Stillbirth		
Primary analysis between internal cohorts	Stillbirths among women with pregnancy outcome data	Women with pregnancy outcome data
Comparison with external comparator (CDC NVSS)	Stillbirths among women with pregnancy outcome data	Live births and stillbirths among women with pregnancy outcome data
Comparison with external comparator (Pfizer Study C4951006)	Stillbirths among women with pregnancy outcome data	Women with pregnancy outcome data
Elective termination		
Primary analysis between internal cohorts	Elective terminations among women with pregnancy outcome data	Women with pregnancy outcome data
Comparison with external comparator (CDC Abortion Surveillance System)	Elective terminations among women with pregnancy outcome data	Live births among women with pregnancy outcome data
Comparison with external comparator (Pfizer Study C4951006)	Elective terminations among women with pregnancy outcome data	Women with pregnancy outcome data
TOPFA		
Primary analysis between internal cohorts	TOPFA among women with pregnancy outcome data	Women with pregnancy outcome data

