Migraines are associated with some baseline pregnancy risks, including pre-eclampsia, and comorbidities, including cardiovascular comorbidities and affective disorders such as anxiety and depression.^{23,24} It will be important to compare the pregnant women with migraine who were exposed to rimegepant and pregnant women with migraine who were unexposed to rimegepant for population differences that may potentially result in differential pregnancy outcomes and the introduction of bias. Additional available, published external data sources in women with migraine, rates from the retrospective pregnancy outcomes study (NDA 212728, post-marketing requirement 3799-7, Pfizer

PFIZER CONFIDENTIAL

study C4951006 (formerly BHV3000-403); representing the pregnant women without migraine cohort), and data from the general population will be evaluated to contextualize observed occurrences of select outcomes in the registry.

An important potential limitation of this pregnancy registry is the possibility of lower-than-expected enrollment. This is possible because rimegepant is not being prescribed to, or used by, women who are or may become pregnant, or because exposed women are not being reported/enrolled into the registry. The feasibility study, planned for the initial 3 years of the study, will help provide an early evaluation of this possibility. If enrollment projections are not being met, it will be important to understand why and to identify additional strategies for increasing registry enrollment and/or identifying additional strategies for evaluating the safety of rimegepant exposure among pregnant women.

Requiring women to be pregnant at the time of enrollment means that SABs occurring early in pregnancy may not be included in the registry. Only recognized SABs occurring after enrollment will be captured. It is important to enroll women as early in pregnancy as possible to maximize the number of prospective enrollments in the registry.

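### SAB, elective termination and preterm birth are compared as simple proportions that do not account for gestational age at entry within the stated windows, or for first rimegepant exposure after enrolment

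*Protocol*

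**What the plan says.** Table 4 (section 9.7.3.3) defines the SAB numerator for the internal comparison as "SABs among women with pregnancy outcome data who are enrolled (and exposed, if applicable) prior to 20 gestational weeks"; the denominator is all women meeting the same condition. The text above the table gives the rule that covers preterm birth as well as SAB: "prevalence will be calculated among the subset of women who are enrolled in the registry prior to 20 and 37 gestational weeks, respectively". Elective termination is "Elective terminations among women with pregnancy outcome data" and stillbirth is "Stillbirths among women with pregnancy outcome data", each over all women with outcome data and with no enrolment or exposure limit. Pre-eclampsia and gestational hypertension use that same denominator.

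The analysis is fixed in section 9.7.3.1: "Exact methods will be used to calculate crude (unadjusted) relative risks for binary outcomes", and for the adjusted result "a weighted generalized linear model using a binomial family and a log (relative risk) link will be employed".

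Other relevant text:
- Section 9.3.1.2 admits women at any gestational age before the outcome.
- Section 9.3.3 counts exposure at any time from conception to outcome.
- Section 9.3.5 lists gestational age at enrolment as a variable; section 9.7.3.4.1 says the listed variables will be considered for the weights.
- Section 9.7.3.5 plans trimester-of-exposure subgroups where numbers allow.
- Section 9.9 acknowledges that "Only recognized SABs occurring after enrollment will be captured".

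**The concern.** Two separate timing problems arise.

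The first is left truncation. A woman enrolled at week 6 and one enrolled at week 19 count equally in the SAB denominator, although the second has almost no SAB risk left. The same holds for preterm birth with entry at week 36, and more strongly for elective termination, where there is no limit. If the cohorts differ in gestational age at entry, the ratio of proportions partly measures entry timing.

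The second is immortal time. A woman may enrol before her first dose. If cohort status follows the definitions in section 9.2.1 (at least one dose in pregnancy, or none), she can join the exposed cohort only by staying pregnant until that dose. A woman who loses the pregnancy first remains unexposed. This pushes the relative risk below 1 and can hide harm.

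There is also a denominator mismatch. Stillbirth, pre-eclampsia and gestational hypertension are defined from about 20 weeks, yet their denominators include pregnancies that ended earlier.

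Table 3 reports power above 99% for SAB, elective termination and preterm birth, so readers will treat these relative risks as informative.

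**Working it through.** **1. The plan's own figures.** Table 3, SAB: n = 390 per cohort, p0 = 0.134, p1 = 2.5 × 0.134 = 0.335, two-sided 0.05. Pooled p = 0.2345. z = [0.201 × √390 − 1.96 × √(2 × 0.2345 × 0.7655)] / √(0.134 × 0.866 + 0.335 × 0.665) = (3.969 − 1.174) / 0.582 = 4.80, so power exceeds 99.9%. Elective termination (>99.9%), preterm birth (99.9%) and stillbirth (12.6%, Fisher) also reproduce. None of these figures is disputed; they describe chance error, not bias.

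**2. Truncation is visible in the planning figures.** The Table 3 rates for SAB, elective termination and stillbirth sum to 13.4% + 18.6% + 0.6% = 32.6% (rough, since denominators differ). Section 9.5.2 assumes 90% live births, so about 10% losses in the registry. Table 4 compares terminations per live birth with the CDC abortion data. Even if every registry loss were a termination, the registry figure is 0.10/0.90 = 11.1%. If the 18.6% is also per live birth, the ratio is at most 11.1/18.6 = 0.60. Section 9.7.3.2 uses exact methods here, so weighting cannot help.

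**3. Unequal entry, no drug effect.** The documents give no entry distribution, so this is an illustration. The weekly SAB hazard is h(w) = h(5) × d^(w−5) for weeks 5 to 19, scaled so that cumulative SAB is 13.4%. Risk remaining from entry week e is R(e) = 1 − ∏(1 − h(w)), w = e to 19. The false relative risk is R(e1)/R(e0).

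| Weekly change in hazard | R(8) | R(10) | R(12) | RR, 8 v 10 | RR, 8 v 12 |
|---|---|---|---|---|---|
| none | 10.87% | 9.15% | 7.39% | 1.19 | 1.47 |
| −15% | 7.95% | 5.44% | 3.59% | 1.46 | 2.21 |
| −24% | 5.96% | 3.39% | 1.87% | 1.76 | 3.19 |
| −30% | 4.73% | 2.31% | 1.10% | 2.05 | 4.29 |

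Reversing the entry order inverts these (0.84 down to 0.23). With 316 women per cohort (the evaluable number in Table 2, borrowed here), the chance of a nominal p < 0.05 for week 8 v 12 is about 33%, 65%, 76% and 78%.

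**4. First exposure after enrolment, no drug effect.** All women enter at week 8. A share f of the would-be exposed take the first dose at a week spread evenly over 9 to 19; losses before that dose count in a comparator of equal initial size. Take the −24% hazard. The mean probability of reaching the first dose is 0.9548. The mean probability of reaching it and then having a SAB is 0.0144.

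- f = 20%. Exposed: (0.8 × 0.0596 + 0.2 × 0.0144) / (0.8 + 0.2 × 0.9548) = 0.0506/0.9910 = 5.10%. Comparator: (0.0596 + 0.2 × 0.0452) / (1 + 0.2 × 0.0452) = 0.0687/1.0090 = 6.81%. RR = 0.75.
- f = 40%. By the same steps, 4.23% v 7.63%. RR = 0.55.

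Across the four hazards, 20% gives 0.83, 0.78, 0.75 and 0.73; 40% gives 0.69, 0.60, 0.55 and 0.53. If late first doses all fall by week 12, the ranges are 0.93 to 0.80 and 0.86 to 0.64.

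**5. Events available for stillbirth and TOPFA.** 390 × 0.00596 = 2.3 and 390 × 0.004 = 1.6 per cohort.

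**The case against.** The strongest reply is that timing is not ignored. SAB and preterm birth have entry and exposure windows, gestational age at enrolment is collected and may enter the weights, covariates still imbalanced may be added to the model, and trimester subgroups are planned. This stands, and a reader who infers that the plan disregards timing altogether goes too far.

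Weighting on entry week would also largely work for left truncation between the internal cohorts. With the −24% hazard, entry spread SD 2 weeks and mean entry 8 v 12, a crude relative risk of about 3 becomes 1.01 after weighting in a large sample (median 1.12 with 316 per cohort). But the covariate is optional, the crude and external comparisons never use it, and weighting on entry week does nothing for immortal time after entry.

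A reader might also infer that the cohorts will enter at different times because they are recruited by different routes. Section 9.2.4.1 describes one campaign aimed at users and prescribers of rimegepant or other migraine therapies. A difference is plausible, since the sponsor's support programme and dispensing pharmacies can reach rimegepant users, but its size cannot be derived.

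Nor does the protocol state that a woman who starts rimegepant after enrolment counts as exposed from enrolment. It has no rule for this case, and the share of such women is unknown.

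The calculated size covers SAB only. It should not be carried over to preterm birth, and for stillbirth the truncation effect is small. Section 9.7 leaves details to the SAP, which is not at hand and may add to this, but the proportion-based method is itself stated in the protocol.

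**Conclusion.** The point holds for SAB, elective termination and preterm birth. The stated method takes no account of gestational age at entry within the windows, or of first exposure after enrolment, and the partial remedies are optional or do not reach the crude and external results.

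For SAB with no drug effect, a 2 to 4 week entry difference gives a relative risk of about 1.2 to 4.3 or the inverse. First exposure after enrolment in 20% or 40% of exposed women gives about 0.75 or 0.55 under the −24% hazard with first doses spread to week 19. The 13.4% is the protocol's rate; the hazard shape, entry weeks, late-starter shares and the classification of late starters are assumptions. These figures show what the method permits and do not predict what will be observed.

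All the outcomes concerned are secondary with nominal p-values, and the primary MCM analysis is not affected by this point. It should be fixed before the final comparative analysis.

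**What to change.** In Table 4 and section 9.7.3.1:

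- **SAB and elective termination:** make the main internal comparison one on the gestational-age scale, with entry at enrolment, rimegepant time-varying from first dose (unexposed before it) and other pregnancy outcomes as competing events. Report weighted hazard ratios or cumulative incidences. Do the same for preterm birth as a supporting analysis.
- **Weights:** make gestational age at enrolment a mandatory covariate for these outcomes.
- **First dose after enrolment:** state how such a woman is classified.
- **Simple proportions, and the external SAB and termination comparisons:** keep them as descriptive, with a left-truncation caveat.
- **Stillbirth, pre-eclampsia and gestational hypertension:** restrict the denominator to pregnancies ongoing at 20 weeks, with exposure before onset.
- **Stillbirth and TOPFA:** do not require hazard models, since about 2 events per cohort are expected.

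The cost is wording and programming. Enrolment, exposure and outcome dates are already collected (section 9.4.1), and section 9.7 reserves comparative analyses for the final analysis. The downside is that hazard ratios or cumulative incidences appear beside relative risks and need explaining.

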9.5.2. Full study

The full study will aim to prospectively enroll a minimum of 390 women with migraine who were exposed to rimegepant during pregnancy or just prior to pregnancy (up to 3 days prior to conception), as well as an internal comparison cohort consisting of 390 women with migraine who were not exposed to rimegepant during pregnancy or just prior to pregnancy (up to 5 product half-lives prior to conception). The target sample size for the registry is based on the primary outcome, MCM, which is also the outcome with the most restrictive denominators and 1 of the lowest prevalence rates in the general population. If all are evaluable for potential MCMs (evaluable being those for whom pregnancy outcome and major/minor congenital malformation assessments are obtained), and assuming an approximate 3% overall population prevalence of MCM, ⁵⁴ at α =0.05, this sample size provides 80% power to detect a 2.5-fold increased risk for overall MCM. Most registry power calculations are performed for overall MCM to detect an increased risk between 2- and less than 3-fold.⁵⁵ A midpoint threshold of a 2.5-fold increased risk was selected for this study. Assumptions for study calculations are consistent with those applied in the retrospective pregnancy outcomes study (NDA 212728, postmarketing requirement 3799-7, Pfizer study C4951006 [formerly BHV3000-403]).

Prospective enrollment can occur only after pregnancy is recognized but while the pregnancy is ongoing. Therefore, early pregnancy losses will not be captured, and a live birth rate higher than that of the general population would be expected. Research shows that approximately 90% of pregnancies enrolled in pregnancy exposure registries result in a live birth.^{56,57} Assuming that 90% of prospectively enrolled pregnancies result in live births and 10% are lost to follow-up,⁵⁸ at α =0.05, the study sample of 390 prospectively enrolled pregnant women in each internal cohort would result in 316 evaluable participants per cohort. Therefore, the study would have 80% power to detect a 2.7-fold increased risk of overall MCM (Table 2).

PFIZER CONFIDENTIAL

Outcome	N per cohort	Reference rate	Relative risk detectable	Power ^b
МСМ	390	3% ^{54,55,59}	2.5	80.6%
МСМ	316 ^a	3% ^{54,55,59}	2.7	80%

Table 2.	Sample Size and Power Estimates for Primary	Outcome, MCM

MCM = major congenital malformation; reference rate = prevalence rate of outcome in general population for pregnant women of any age

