^a Assumes that 90% of prospectively enrolled pregnancies result in live births and 10% are lost to follow-up, resulting in 316 evaluable participants

^b Power calculations based on normal approximation, 2-tailed, α =0.05⁶⁰

Additionally, Table 3 shows that, without any adjustments for multiple comparisons, the proposed sample size (390 pregnant women) will afford the study >80% power to detect a 2.5-fold increase in all other outcomes except eclampsia, stillbirth, and TOPFA (for which the study will have <20% power to detect a 2.5-fold increase).

Table 3.	Power Calculations
----------	---------------------------

Outcome	Reference rate	Power estimate ^a
MCM ^{54,55,59}	3%	80.6%
Gestational diabetes ²⁹	6.9%	>99.0%
Gestational hypertension ⁶¹	6.5%	>99.0%
Pre-eclampsia ⁶²	3.40%	85.5%
Eclampsia ⁶¹	0.3%	2.7% ^b
SAB ⁶³	13.4%	>99.0%
Stillbirth ⁶⁴	0.596%	12.6% ^b
Elective termination ⁶⁵	18.6%	>99.0%
TOPFA ⁶⁶	0.4%	5.8% ^b
Preterm birth ²⁹	8.47%	>99.0%
SGA*	10.0%	>99.0%
Postnatal growth deficiency*	10.0%	>99.0%

MCM = major congenital malformation; reference rate = prevalence rate of outcome in general population for pregnant women of any age; SAB = spontaneous abortion; SGA = small for gestational age; TOPFA = termination of pregnancy for fetal anomaly.

*By Definition

^a Power calculations were conducted using nQuery and were based on normal approximation, 2-tailed, alpha 0.05.

^b Fisher's Exact test was used for power calculation.

PFIZER CONFIDENTIAL

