9.7.3.2. Comparison with external comparators

Analyses will also be conducted to compare the prevalence rates of the outcomes of interest among rimegepant-exposed participants of the main analysis population with those of selected external comparators (eg, MACDP, EUROCAT, NVSS), if available. Prevalence rates of the outcomes of interest will be calculated as described in Section 9.7.3.3. These registry prevalence rates will then be compared with those of selected external comparators using Exact methods. Prevalence rates will be reported along with their 95% CIs and p-values for the comparison.

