For comparison with external comparators, the prevalence rates of the outcomes of interest among the rimegepant-exposed participants of the main analysis population will be calculated according to the conventions used by the selected external comparators. For example, for the comparison with MACDP, live births and stillbirths with MCMs (including MCMs not associated with medication exposure) will be included in the numerator, and the denominator will be the number of live births. The MACDP calculates rates by this convention, which increases sensitivity. Likewise, for comparisons with the external cohort of pregnant women without migraine (from the retrospective pregnancy outcomes study), the conventions used to calculate outcome prevalence rates in the internal and external cohort will be aligned.

In addition, "crude" prevalence rates, without limitations and exclusions, may be conducted to avoid restricting the main analysis population (denominator). For example, infants with MCM and/or infants born preterm may be included for the prevalence rate calculation of infant developmental delay.

Outcome	Numerator	Denominator	
Primary Outcome – MCM			
Primary analysis: among live births with 1 st trimester exposure (if applicable for cohort)	Live births with confirmed MCMs (excluding MCMs not associated with medication exposure) among women with pregnancy outcome data and exposure during 1 st trimester (if applicable)	Live births among women with pregnancy outcome data and, if applicable, exposure during 1 st trimester	
Secondary analysis: among all pregnancy outcomes with 1 st trimester exposure (if applicable for cohort)	Live births and fetal losses with confirmed MCMs (excluding MCMs not associated with medication exposure) among women with pregnancy outcome data and, if applicable, exposure during 1 st trimester	Live births and fetal losses among women with pregnancy outcome data and, if applicable, exposure during 1 st trimester	
Secondary analysis: among live births with exposure at any time during pregnancy (if applicable for cohort)	Live births with confirmed MCMs (excluding MCMs not associated with medication exposure) among women with pregnancy outcome data and, if applicable, exposure at any time during pregnancy	Live births among women with pregnancy outcome data and, if applicable, exposure at any time during pregnancy	

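### The planned p-value for elective termination against CDC Abortion Surveillance tests a null of 18.6 per 100 live births, while the protocol's own 90% live-birth assumption caps the registry ratio at about 11.1, so the p-value is uninformative at plausible rates and leans towards false reassurance.

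*Protocol*

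**What the plan says.** In Section 9.7.3.3, Table 4 gives three comparisons for elective termination: between the internal cohorts, with Study C4951006, and a row headed "Comparison with external comparator (CDC Abortion Surveillance System". In the CDC row the numerator is elective terminations and the denominator is "Live births among women with pregnancy outcome data". The text of the same section says that registry rates for external comparisons "will be calculated according to the conventions used by the selected external comparators".

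Section 9.7.3.2 sets the inference: "These registry prevalence rates will then be compared with those of selected external comparators using Exact methods", and "Prevalence rates will be reported along with their 95% CIs and p-values for the comparison".

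The only reference value in the protocol is in Table 3 of Section 9.5.2: "Elective termination ⁶⁵ 18.6% >99.0". Its citation is the CDC abortion surveillance report.

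Section 9.5.2 also says that "approximately 90% of pregnancies enrolled in pregnancy exposure registries result in a live birth". It explains that enrolment follows recognition of the pregnancy, so a live-birth rate above that of the general population is expected. The evaluable sample is then derived by "Assuming that 90% of prospectively enrolled pregnancies result in live births and 10% are lost to follow-up".

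**The concern.** The CDC comparison asks whether women in the registry terminate as often, per live birth, as the surveillance figure. That is not the same as asking whether rimegepant changes the termination rate. The registry enrols volunteers whose pregnancies are recognised and ongoing, and the protocol itself expects 90% of them to end in live birth. On that figure the null value is out of reach before any data are collected.

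The protocol carries the enrolment-timing argument through for spontaneous abortion, where the denominator is limited to women enrolled before 20 weeks, and Section 9.9 repeats it for early spontaneous abortions. It makes no such provision for elective termination.

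At stake is a line in the final safety report showing a highly significant, lower-than-background termination rate in exposed women that comes from enrolment timing and selection. A reader could take it as evidence of safety.

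**Working it through.** **Inputs.** 390 enrolled per cohort, 10% lost to follow-up, 90% live births (Section 9.5.2); reference 18.6% (Table 3). Assumed: two-sided alpha 0.05, which the protocol states for its power calculations but not for this test; 18.6% read as terminations per live birth, from the shared CDC source and the Table 4 denominator. The share of non-live outcomes that are elective terminations is not given, so it is varied. Two anchors in the protocol are the Table 3 rates for termination and spontaneous abortion, 18.6/(18.6 + 13.4) = 58%, and the clinical programme in Section 7.2 (3 elective, 6 spontaneous), 3/9 = 33%.

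**The plan's own figures reproduce.** 390 × 0.9 × 0.9 = 315.9, or 316. Power for malformations is 80.6% (390 per cohort, 3% v 7.5%) and 80.1% (316 per cohort, 3% v 8.1%). Power for elective termination at 18.6% v 46.5% exceeds 99%.

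**Ceiling on the ratio.** Known outcomes: 390 × 0.9 = 351. Live births: 316. Non-live outcomes of every kind: 35. The largest possible ratio is 0.10/0.90 = 11.1% (35/316), against a null of 18.6%. To reach 18.6% with no spontaneous abortion or stillbirth at all, the live-birth share would have to fall to 1/1.186 = 84.3%.

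**Test at the ceiling.** With 316 live births, an exact binomial test against 0.186 calls 45 or fewer terminations significantly low (45/316 = 14.2%). At 35/316 the two-sided p is 0.0004.

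**Probability of a significantly low result, 351 outcomes, 90% live births:**

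| Terminations as share of non-live outcomes | Exact binomial, T/L | Exact Poisson | Binomial, T/(T+L) v 0.157 |
|---|---|---|---|
| 100% | 92.9% | 90.3% | 87.1% |
| 90% | 98.2% | 97.0% | 95.7% |
| 75% | 99.9% | 99.8% | 99.6% |
| 58% or less | >99.9% | >99.9% | >99.9% |

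T is terminations and L live births, with both varying at random. Holding live births at 316 gives 96.5% in the first row. The most favourable case therefore spans 87-97%.

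**Doubling.** If terminations rise from 2% to 4% of pregnancies, the expected count goes from 351 × 0.02 = 7 to 351 × 0.04 = 14. Both are far below the cut-off of 45, and both are called significantly low in about 100% of cases.

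**Larger effects (316 live births fixed).**
- Starting at 5.6 per 100 live births (50% share), a doubling is still called low in 96% of cases and a 2.5-fold rise in 61%.
- Starting at 6.5 (58% share), the figures are 79% and 20%.
- Starting at the 11.1 ceiling, a doubling is called low in 0.02% and high in 33%.

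**Sensitivity to the 90% (exact binomial, T/L, 351 outcomes).**
- At 88% live births: 60% if all non-live outcomes are terminations, 97% at a 75% share, over 99% at a 58% share.
- At 86%: 19% and, at a 58% share, 99%.

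**Other reading of 18.6%.** If it is a share of pregnancies, 50 or fewer of 351 is significantly low. With 10% terminated, that happens in 99.5% of cases.

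**Form of the test.** Terminations are not a subset of live births. If the population ratio really were 0.186 and the test were a binomial with live births as trials, it would reject in 8.8-10.2% of cases at nominal 5% (284 to 390 terminations plus live births). Testing T/(T+L) against 0.186/1.186 = 0.157 rejects in about 4%.

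**The case against.** The strongest reply is that little depends on this p-value. Elective termination is a secondary outcome, Section 9.7 calls secondary p-values nominal, and published external data are described as supplemental (Section 9.2.3.3) and as context (Section 9.9). Formal relative-risk inference is between the internal cohorts. Study C4951006 provides an external comparison with women as denominator, and termination for fetal anomaly is analysed separately. The protocol also acknowledges the high live-birth rate and the unrepresentativeness of volunteers. All of that stands and limits the weight of the point. It does not repair the comparison: nominal status concerns multiplicity, and neither caveat is applied to this row.

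Three stronger readings are tempting, and the documents do not support them.
- A reader might infer that the result is fixed whatever the drug does. It is not: large increases escape, as shown above.
- A reader might infer an unconditional floor of 93%. That floor needs the approximate 90% planning figure and one particular exact test. It is 87% with T/(T+L) and 60% at 88% live births when every non-live outcome is a termination.
- A reader might infer that the plan fixes a test with the wrong variance. Section 9.7.3.2 says only that exact methods will be used, so the 9-10% error rate applies only if a binomial with live births as trials is meant.

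It is also fair that the protocol does not state outright that 18.6% is per live birth, or that this value will be the reference at the final analysis.

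**Conclusion.** The point holds in conditional form. Under the protocol's own planning figure the null for this test is excluded in advance by enrolment timing and selection. The direction is robust: at a 58% termination share the low result appears in over 99% of cases at 90% and 88% live births, under every exact test tried. Only with almost no spontaneous abortions or stillbirths, and a live-birth share below 90%, does it weaken materially. The p-value is uninformative at plausible termination rates, and its error leans towards reassurance.

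This rests on 18.6% as the reference, about 90% live births, 351 known outcomes and two-sided alpha 0.05. It concerns one secondary, nominal external comparison. It should be changed, but it does not threaten the primary objective.

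**What to change.** In Section 9.7.3.2 and the CDC row of Table 4, drop the p-value for elective termination against CDC Abortion Surveillance. Report the registry ratio with its CI descriptively, state that the two sources are not comparable because registry enrolment is prospective and voluntary, and base inference on the internal cohort.

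If a test of a ratio r is kept, specify terminations out of terminations plus live births against r/(1+r), which is 0.157 for r = 0.186. This settles the variance but leaves the null misplaced, so the comparability statement is still needed.

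The cost is a sentence in Section 9.7.3.2, one table row and the loss of one p-value.
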